9.2.7 End of Observation Visit

The End of Observation Visit is defined as a visit at completion of the 15-month observation period, or at the end of 1st line treatment; whichever occurs first. The End of Observation Visit is also defined as a last visit before death, withdrawal of consent, or lost to follow-up; whichever occurs first.

The following data will be collected at the End of Observation Visit:

- Adverse events: type and duration of AE; prophylaxis treatment for skin toxicity, occurrence of skin toxicity and details of skin toxicity management using FACT - EGFRI-18 QoL questionnaire (See Appendix F) if permitted in a country per local regulations.
- All other safety events with the exception of the protocol exempted events.
- Date and reason for ending study:
 - 15-month observation period reached (measured from the enrolment visit)
 - start of 2nd line treatment
 - death date and primary cause of death to be recorded
 - lost to follow-up
 - withdrawal of informed consent
- Tumour evaluations using all or any of the following methods: CT, MRI, PET, chest X rays, bone X rays, ultrasound assessments (any performed) or radio nuclear examinations
- Resection status as applicable.

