Immunoglobulin	
institutional review board	
IR (irinotecan) OX (oxaliplatin)	
interactive voice response system	
Kirsten rat sarkoma 2 viral oncogene homolog, gen of RAS family	

Product: Panitumumab (Vectibix®) Protocol Number: 20170734 POWER Date: 29 April 2019

Date: 29 April 2019 Page 9 of 64

Abbreviation or Term	Definition/Explanation	
LV	Leucovorin, folinic acid	
mCRC	metastatic colorectal cancer	
MedDRA	Medical dictionary for regulatory activities	
MRI	magnetic resonance imaging	
NRAS	neuroblastoma RAS viral oncogene homolog, gene of RAS family	
ORR	objective response rate	
OS	overall survival	
OTC	over the counter	
PET	positron emission tomography	
PFS	progression-free survival	
PP	percentage points	
QoL	quality of life	
RECIST	response evaluation criteria in solid tumours	
RR	response rate	
SAP	statistical analysis plan	
SmPC	summary of product characteristics	
TGFα	transforming growth factor-alpha	
TNM	tumour node metastasis	
WT	wild type	
VEGF	vascular endothelial growth factor	
VEGFR	vascular endothelial growth factor receptor	
5-FU	fluorouracil	
Baseline Visit	The date of start of 1st line chemotherapy and panitumumab	
Enrolment Visit	The date of informed consent signature	
End of Observation Visit	The visit at the end of Prospective Observation Period or the last visit before death or withdrawal of informed consent or lost to follow-up	
End of Study Visit	The visit at the end of Safety Follow-up or at the end of Prospective Observation Period if panitumumab was not administered in the last 4 weeks of observation	
Prospective Observation Period	Period between Enrolment and start of Safety Follow-up defined as 1) 15 months of continuous 1st line panitumumab plus chemotherapy treatment administration or 2) up to 15 months after stop of 1st line treatment without subsequent 2nd line treatment or 3) 1st line panitumumab plus chemotherapy until progression/start of 2nd line treatment or death or withdrawal of informed consent or loss-to follow-up, whichever occurs first	

Product: Panitumumab (Vectibix®) Protocol Number: 20170734 POWER Date: 29 April 2019

Date: 29 April 2019 Page 10 of 64

Abbreviation or Term	Definition/Explanation
Retrospective Period	Period between start of 1 st line panitumumab plus chemotherapy and enrolment

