9.1 Study Design

This is a multicentre, ambidirectional (retrospective-prospective), observational study in the selected European countries, including but not limited to Austria, Bulgaria, Croatia, Czech Republic, Hungary, Poland, Slovenia, Romania and Russia.

The Study Design Schema is presented in Figure 1. In general, to gather the most comprehensive and recent data, the study consists of 3 phases: Retrospective Period, Prospective Observation and Safety Follow-up. Retrospective data will be collected from

Date: 29 April 2019 Page 22 of 64

1 to a maximum of 12 months preceding enrolment, Prospective Observation will be led by a maximum of 15 months and a Safety Follow-up of 30 days after the end of the observation, giving a total of a maximum 28 months of mCRC management data.

Subjects with initially non resectable WT *RAS* mCRC receiving panitumumab in combination with chemotherapy as first-line treatment will be eligible for the study. The decision on treatment with panitumumab should have been taken independently and prior to the decision to study enrolment.

Study participants must have received at least one dose of panitumumab in combination with chemotherapy between 1 and 12 months before enrolment (defined as the informed consent [ICF] signature date). Panitumumab as a 1st line treatment in combination with

chemotherapy should be ongoing at enrolment. Therefore, the Retrospective phase will last a maximum of 12 months for an individual subject. An Interactive voice response system (IVRS) system will be used for enrolment. Baseline data including demographics, characteristics and subjects' clinical information will be collected retrospectively from medical records up to the point of enrolment. From the enrolment point, prospective data will be recorded. The Prospective phase will consist of two periods: 1) observation during the 1st line treatment administration and 2) observation after the end of 1st line treatment. The maximum duration of the Prospective phase will be 15 months. In case of a change in therapy and 2nd line treatment implemented, subjects will enter into the Safety Follow-up phase.

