9.2.6 Prospective Observation Period

The Prospective Observation Period will start at the enrolment Visit and subject visits should be registered on a monthly basis. Data will be collected on a monthly basis for 15 months during 1st line treatment administration. In case of earlier discontinuation of 1st line treatment, the data from maintenance treatment (other than 2nd line treatment) will be collected for the Observation Period of 15 months.

Data obtained during the 15-month Observation Period will be reported into the eCRF.

The following data will be collected on a monthly basis:

- Physical measurement
- Vital signs
- ADR events: type and duration of ADR incident; prophylaxis for skin toxicity, occurrence of skin toxicity and details of skin toxicity management using FACT EGFRI-18 QoL questionnaire (See Appendix F) if permitted in a country per local regulations.
- Concomitant medications
- 1st line treatment pattern including:
 - chemotherapy: drug, dosage and interval
 - changes in dosing and reasons for the change
 - treatment interruption if it is longer than 30 days in one single interval and reason of interruption
 - changes in biologic treatment (both chemotherapy and targeted therapy) for any reason
 - stop date and reason for treatment discontinuation.
- 2nd line treatment pattern including:
 - biological agents: drug name/s, dose and schedule
 - chemotherapy: drug name/s, dosage and interval
- Panitumumab administration:
 - dose and schedule
- Laboratory values: haematology and chemistry

Date: 29 April 2019 Page 29 of 64

- ECOG performance status
- Tumour evaluations:
 - evaluation and re evaluation / assessment (methods, criteria, timing Q2M), RECIST criteria (if available)
 - ETS at week 8 (if available, as per clinical practice) measured using all or any of the following methods: CT, MRI, PET
 - disease evaluation as routinely monitored (if different than RECIST criteria), including chest X rays, bone X rays, ultrasound assessments (any performed) or radio nuclear examinations
 - information about biomarker status (if available).

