9.2.8 Safety Follow-up

Safety follow-up will last approximately 30 days after the start of 2nd line treatment, or after 15 months of observation if panitumumab was administered in the last 4 weeks of observation, whichever occurs first, except for death, withdrawal of consent or lost to follow-up.

Date: 29 April 2019 Page 30 of 64

The following data, at the End of Observation Visit will be collected where available and recorded as standard clinical practice:

- Adverse Events: type and duration of AE incident; occurrence of skin toxicity and details of skin toxicity management using FACT- EGFRI-18 QoL questionnaire (See Appendix F) if permitted in a country per local regulations.
- All other safety events with the exception of the protocol exempted events.
- Concomitant medications
- Laboratory values: haematology and chemistry
- Tumour evaluations:
 - evaluation and re evaluation / assessment (methods, criteria, timing Q2M), RECIST criteria (if available)
 - ETS at week 8 (if available) measured using all or any of the following methods: CT, MRI, PET
 - disease evaluation as routinely monitored (if different than RECIST criteria), including chest X rays, bone X rays, ultrasound assessments (any performed) or radionuclear examinations
 - information about biomarker status (if available).

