Appendix E. Schedule of Assessments

Data to be collected	Baselinea	Observation Period									
		Monthly follow-up dateb	Safety follow up ^o	End of Study							
Enrollment	x										
Demographics	x										
Targeted medical history	×										
Physical measurement	x	x									
Vital Signs	x	x									
Events (Observational study)		x	х	x							
Concomitant medications	x	x	х	х							
1st line of treatment	×	x									
2 nd line of treatment		x									
Panitumumab administration	x	x									
Substance use	x										
Laboratories	x	x	х								
Reproductive status	x										
ECOG performance status	x	x									
Disease history	x										
Tumor evaluations	x	x	х								
Site characteristics	×										

^aBaseline will be from 1 to maximum 12 months preceding enrolment in the study

[figure not shown]

Data will be collected for 15 months

[°]This is 30 days after the end of 1st line of treatment

Date: 29 April 2019 Page 62 of 64

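### Section 9.2.7 closes observation at the end of 1st line treatment, while Sections 2, 9.1 and 9.2.6 continue it to 15 months, and the Appendix E footnote shifts Safety Follow-up in the same way

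*Protocol*

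**What the plan says.** Two places make the end of 1st line a boundary:

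- Section 9.2.7, first sentence: the End of Observation Visit is "a visit at completion of the 15-month observation period, or at the end of 1st line treatment; whichever occurs first".
- Appendix E, footnote to the Safety Follow-up column: "This is 30 days after the end of 1st line of treatment".

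The rest of the protocol does not:

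- Section 9.1 splits the prospective phase into "observation during the 1st line treatment administration and 2) observation after the end of 1st line treatment", caps it at 15 months, and sends subjects to Safety Follow-up when 2nd line is implemented.
- Section 9.2.6: "In case of earlier discontinuation of 1st line treatment, the data from maintenance treatment (other than 2nd line treatment) will be collected", and this runs for the 15-month observation period.
- Section 2, Safety Follow-up definition: it recognises subjects who complete 15 months of observation with a shortened 1st line and no 2nd line, and exempts them from Safety Follow-up.
- Section 2, End of Observation Visit definition: it refers to the end of the Prospective Observation Period, death, withdrawal or loss to follow-up, not to the end of 1st line.
- Section 9.2.7, list of reasons for ending: "15-month observation period reached (measured from the enrolment visit"), start of 2nd line, death, loss to follow-up and withdrawal. Neither the end of 1st line nor progression is listed.
- Section 9.2.8: "Safety follow-up will last approximately 30 days after the start of 2nd line treatment", or after 15 months if panitumumab was given in the last 4 weeks.

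The Section 2 definition of the Prospective Observation Period is loosely worded. One limb reads "up to 15 months after stop of 1st line treatment without subsequent 2nd line treatment", and another joins progression and the start of 2nd line with a slash.

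**The concern.** A site that follows the first sentence of 9.2.7 stops recording when 1st line stops, whatever the reason. For a subject who stops for toxicity or after resection, everything later is missing.

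- **Primary objective.** Describing 2nd line therapy is part of it (Section 8.1). Detail on 2nd line is collected only in the monthly period (9.2.6, and the monthly column of Appendix E). The visits in 9.2.7 to 9.2.9 do not collect it, apart from the start of 2nd line as an end reason. If monthly entry closes at the end of 1st line, a 2nd line begun some months later is never described.
- **Secondary outcomes.** Death and progression go into Kaplan-Meier analyses (9.7.2.4). Stopping 1st line is plausibly related to prognosis, so censoring at the stop is plausibly informative. Conversion to resectability is a plain proportion and depends directly on how long subjects are watched.

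The loss arises at data collection, so no later analysis plan can repair it.

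**Working it through.** The point rests on comparing the text. The protocol states no figure for it that could be reproduced.

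**Step 1. Apply each rule to one subject.** The subject stops 1st line *s* months after enrolment, progression-free, with no 2nd line, and stays alive and in contact.

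| Rule | End of prospective observation | s = 3 | s = 9 |
|---|---|---|---|
| 9.2.7, first sentence | min(15, s) | 3 | 9 |
| 9.1, 9.2.6 and the 9.2.7 reason list | 15 | 15 | 15 |
| Follow-up lost under 9.2.7 | 15 − s | 12 | 6 |

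The two rules cannot both be followed for any s below 15. A site that closes the subject at s also finds no matching reason in the list.

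**Step 2. Safety Follow-up for the same subject.** Under the Appendix E footnote it falls 30 days after month s. Under 9.2.8 it would start at month 15, and only if panitumumab was given in the preceding 4 weeks. Under Section 2 this subject has none. The footnote therefore includes a group that Section 2 exempts.

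**Step 3. Progression that would not be seen.** Inputs: s = 3; 15-month cap (Section 9.1); median time to progression m, which the protocol does not give, taken as 8 to 12 months; exponential times. Given no progression at the stop, the chance of progression in the remaining 15 − 3 = 12 months is 1 − 2^(−12/m):

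- m = 12: 1 − 2^(−1) = 50%
- m = 10: 1 − 2^(−1.2) = 56%
- m = 8: 1 − 2^(−1.5) = 65%

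Under 9.2.7 the corresponding figure is 0%, because observation has closed. With an exponential time it makes no difference whether the median is counted from baseline or from enrolment.

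The unconditional chances 1 − 2^(−3/m) and 1 − 2^(−15/m), which are 19% and 65% at m = 10, are not the right comparison. They include subjects who progressed before stopping, and 9.2.7 does not lose those events.

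**The case against.** The outliers are one sentence and one footnote. Everything else, including the reason list in the same section as the sentence, points to 15 months from enrolment or the start of 2nd line. Section 9.6 provides protocol-specific training and an eCRF completion guideline, and the study is descriptive, with death and progression as secondary outcomes. This stands as far as it goes: many sites may do the intended thing. But the section a site consults when closing a subject is the one with the wrong sentence, and the schedule of assessments supports it.

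Four stronger readings are tempting and are not supported:

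- *Observation could run 15 months beyond the stop of 1st line*, to month 18 for the subject above. Section 2 says only up to 15 months, Sections 9.1 and 9.2.1 cap the prospective phase at 15 months, and the 28-month total in 9.1 is 12 + 15 + 1. The wording is loose rather than a separate rule.
- *The limb "15 months of continuous 1st line panitumumab plus chemotherapy treatment administration" could leave a subject enrolled at month 12 with only 3 more months.* The Section 2 definition begins at enrolment, and 9.2.7 measures the 15 months from the enrolment visit.
- *Ending at progression loses progressions.* It does not lose the event itself. It shortens follow-up for death and for 2nd line choice.
- *Country comparisons are confounded by follow-up length.* Country is an exposure variable in Table 2, so this would follow if countries applied different rules, but nothing in the protocol shows that they would.

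**Conclusion.** The protocol contradicts itself on when observation ends for a subject who stops 1st line early without 2nd line, and on when that subject's Safety Follow-up starts. As written, the first sentence of 9.2.7 and the Appendix E footnote are incompatible with Sections 2, 9.1, 9.2.6 and 9.2.8 and with the end reasons in 9.2.7.

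For a progression-free stop at month 3, the cost is 12 of 15 months of follow-up and about 50% to 65% of such subjects with a progression that goes unseen. That range rests on an assumed median of 8 to 12 months and exponential times. The text conflict needs neither assumption. The effect on the whole study depends on how many subjects stop 1st line progression-free and how many sites follow 9.2.7. The protocol gives neither number, so no study-level bias is claimed.

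**What to change.** Remove the end-of-1st-line alternative from the first sentence of 9.2.7. State one data-collection rule throughout, the one already in 9.1, 9.2.6 and the 9.2.7 reason list: observation runs from enrolment to the earliest of 15 months, start of 2nd line, death, withdrawal or loss to follow-up, with progression recorded as an event rather than an end. Reword the Section 2 definition of the Prospective Observation Period to match, both in the limb counted from the stop of 1st line and in the limb that joins progression to the start of 2nd line.

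Reconcile the Appendix E footnote with Section 2, 9.1 and 9.2.8 on the start of Safety Follow-up. Which anchor applies is for the sponsor to decide.

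The cost is a text amendment and a site notice, plus reopened monthly entry for any subject already closed at the end of 1st line. The change does not extend follow-up for death past the start of 2nd line. That limit belongs to the design and remains.

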9.2.8 Safety Follow-up

Safety follow-up will last approximately 30 days after the start of 2nd line treatment, or after 15 months of observation if panitumumab was administered in the last 4 weeks of observation, whichever occurs first, except for death, withdrawal of consent or lost to follow-up.

Date: 29 April 2019 Page 30 of 64

The following data, at the End of Observation Visit will be collected where available and recorded as standard clinical practice:

- Adverse Events: type and duration of AE incident; occurrence of skin toxicity and details of skin toxicity management using FACT- EGFRI-18 QoL questionnaire (See Appendix F) if permitted in a country per local regulations.
- All other safety events with the exception of the protocol exempted events.
- Concomitant medications
- Laboratory values: haematology and chemistry
- Tumour evaluations:
 - evaluation and re evaluation / assessment (methods, criteria, timing Q2M), RECIST criteria (if available)
 - ETS at week 8 (if available) measured using all or any of the following methods: CT, MRI, PET
 - disease evaluation as routinely monitored (if different than RECIST criteria), including chest X rays, bone X rays, ultrasound assessments (any performed) or radionuclear examinations
 - information about biomarker status (if available).

9.2.9 End of Study Visit

At the end of the Safety Follow-up Period or after reaching the end of 15-month observation period if panitumumab was not administered in the last 4 weeks of observation, the End of Study Visit should be performed.

The following data will be collected:

- safety events per protocol
- · concomitant medications.

9.3 Variables

The list of variables for each objective is summarized in Table 2. described in the section 9.3.2 below.

9.3.1 Exposure Assessment

Exposure will be calculated taking into account both Retrospective and Prospective phases of the study and in line with the study design, will cover all subjects who received at least one infusion of panitumumab in combination with chemotherapy as a 1st line treatment prior to enrolment. The time of exposure will be counted from the date of the first dose of 1st line chemotherapy and panitumumab (Baseline) to the date of discontinuation of 1st line treatment. The number of doses of panitumumab in combination with chemotherapy received during exposure will be collected. The exact dates of receiving doses will not be collected.

Date: 29 April 2019 Page 31 of 64

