Safety Follow-up will last approximately 30 days after the start of 2nd line treatment, or after 15 months of observation if panitumumab was administered in the last 4 weeks of observation, whichever occurs first, except for death, withdrawal of consent or lost to follow-up. If a subject receives panitumumab in combination with chemotherapy for 15 months, then 30 days of Safety Follow-up will be the 16th month of observation.

Date: 29 April 2019 Page 23 of 64

Table 2. Objectives and Outcomes

Objectives	Outcomes	Exposure variables
Primary		
To obtain characteristics of subjects with WT RAS non resectable mCRC receiving panitumumab in combination with chemotherapy as a 1 st line treatment.	 Demographics Disease history, including location of tumour (left vs. right side) Current status of disease 	Country Total
To describe the patterns of treatment , including 1 st and 2 nd line therapies.	 1st line treatment Any changes during 1st line treatment, including dose, infusion schedule, and reasons for changes Type of progression leading to 2nd line choice Type of 2nd line treatment (type of anticancer therapy) 	 Country Location of tumour (left vs. right side) Oxaliplatin-based chemotherapy Irinotecan-based chemotherapy Total
	 Dose, schedule and reason for treatment selection Subsequent treatment line/approach 	D 1

Page 1 of 2

Date: 29 April 2019 Page 24 of 64

Objectives	Outcomes	Exposure variables
Secondary		
To assess the response to 1 st line treatment described by: the relationship between death, disease progression, ETS (if available), and subject characteristics with the particular interest in tumour location	 Death Disease Progression Response rate Rate of conversion to resectable mCRC Tumour markers: CEA and CA 19.9 Early tumour shrinkage (if available) 	Country Location of tumour (levs. right side) Current disease status Oxaliplatin-based chemotherapy Irinotecan-based chemotherapy Total
To assess incidence of adverse drug reactions (ADR) events (general)	ADR reports: type and duration of ADR incident	Country Total
Exploratory (if available)		

Date: 29 April 2019 Page 25 of 64

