 - evaluation and re evaluation / assessment (methods, criteria, timing Q2M), RECIST criteria (if available)
 - ETS at week 8 (if available, as per clinical practice) measured using all or any of the following methods: CT, MRI, PET
- Site characteristics.

Safety data will not be collected retrospectively, however side effects related to panitumumab treatment, and details of skin toxicity management will be collected as part of medical history.

Date: 29 April 2019 Page 28 of 64

The following key data will also be collected at Baseline where available. These data must originate from the time prior to the subjects' first dose of panitumumab in combination with chemotherapy:

 Method (incl. Brand name, if available) and date of RAS testing (test requested and result available), if available. Data on other biomarkers, if conducted, will also be collected.

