9.7.3 Analysis of Safety Outcomes

Number of subjects with serious and non-serious ADRs leading to discontinuation of panitumumab and serious ADRs associated with fatal outcomes will be tabulated by system organ class and preferred term.

Measures of skin toxicity management (FACT- EGFRI-18 QoL questionnaire (See Appendix F) if allowed per local regulations), type of measures, duration, severity of skin toxicity, and type of treatment will be summarized.

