11.1.5.1 Prospective Observational Period

This study is collecting information from subjects ambidirectionally (retrospectively-prospectively). All safety events (adverse events, product complaints, and other safety findings) considered to have occurred following subject exposure to panitumumab will be collected from signing of informed consent form with the exception of the protocol exempted events listed in appendix G to final study contact. The Investigator is responsible for ensuring that all safety events they become aware of during study period, are recorded in the subject's appropriate study documentation. Those safety events which are considered serious must also be submitted as individual safety reports to Amgen Safety via the applicable Amgen Safety Reporting Form (paper or electronic form) within 1 business day of Investigator awareness. Non-serious Adverse Events (AEs) must be reported in an expeditious manner, not to exceed 15 calendars days of Investigator awareness.

If the electronic data capture (EDC) system is unavailable to the site staff, the adverse event which is considered serious must still be reported to Amgen within 1 business day of Investigator's awareness using the paper Adverse Event Contingency Report Form. For EDC studies where the first notification of an Adverse Event is reported to Amgen via the Adverse Event Contingency Report Form, the data must be entered into the EDC system when the system is again available. Non-serious Adverse Events (AEs) must be

Date: 29 April 2019 Page 44 of 64

reported in an expeditious manner, not to exceed 15 calendars days of Investigator awareness.

See Appendix B and Appendix D Additional Safety Reporting Information. The Investigator may be asked to provide additional information for any event submitted, which may include a discharge summary or extracts from the medical record. Information provided about the event must be consistent with information recorded in the study documentation where safety data may also be recorded.

Protocol Exempted Events

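### ADR incidence is summarised as a number of subjects although ADR observation lasts from weeks to about 16 months, and the only exposure time defined does not match the ADR window

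*Protocol*

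**What the plan says.** **Objective.** Protocol 8.2 makes ADR incidence a secondary objective. Table 2 (section 9.1) gives the outcome as "ADR reports: type and duration of ADR incident" and breaks it down by Country and Total.

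**Planned summary.** Section 9.7.3 states: "Number of subjects with serious and non-serious ADRs leading to discontinuation of panitumumab and serious ADRs associated with fatal outcomes will be tabulated". The rows of that table are system organ classes and preferred terms. The section names no denominator and no time at risk. Section 9.7.2.1 adds percentages for categorical outcomes in general, and 9.7.2.3.1 puts every eligible enrolled subject into all summaries.

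**ADR collection.** Under 11.1.5.1, safety events in treated subjects "will be collected from signing of informed consent form with the exception of the protocol exempted events", and this goes on until the last study contact. Section 9.2.5 says: "Safety data will not be collected retrospectively, however side effects related to panitumumab treatment" are, together with details of skin toxicity management, recorded as medical history.

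**Timing.** Consent falls 1 to 12 months after the first dose (9.2.1, 9.2.3.1). Prospective observation lasts at most 15 months and ends earlier at the start of 2nd line treatment, death, withdrawal or loss to follow-up (Section 2, 9.1). A 30-day Safety Follow-up is added where it applies.

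**Exposure.** Section 9.3.1 covers both the retrospective and the prospective phase: "The time of exposure will be counted from the date of the first dose of 1st line chemotherapy and panitumumab (Baseline". The count stops when 1st line treatment is discontinued. On individual infusions the section says: "The exact dates of receiving doses will not be collected".

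**The concern.** A subject observed for 15 months has more chance of a recorded ADR than one observed for 3. A number of subjects, or a percentage of all enrolled, therefore mixes the risk of an ADR with the time in which one could be recorded. Two countries with the same underlying risk can show different figures if one enrols subjects later in treatment or follows them for less time.

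The absence of a hypothesis test does not remove the problem, because in a descriptive study the estimates are the product. Summaries per country are planned (9.7.1), the abstract says that proportions and intervals are most useful in subgroups, and reimbursement agencies are named as users (9.5). Section 7.2 already sets a rash prevalence of 49% from observational studies against randomised-trial expectations, so the new figures are likely to be compared in the same way.

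An analyst who wants to allow for unequal observation will look for an exposure time. The protocol offers one, and its window is not the window in which ADRs are collected.

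**Working it through.** **1. The protocol's own figure.** The abstract gives a 95% CI half-width of no more than 4 percentage points for 600 subjects. At a proportion of 0.5, 1.96 × √(0.25/600) = 0.0400, so it reproduces. It describes sampling error only and does not bear on unequal observation time.

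**2. The two windows side by side.**

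| | Starts | Ends |
|---|---|---|
| Exposure (9.3.1) | first dose | discontinuation of 1st line |
| ADR collection (11.1.5.1) | consent, 1 to 12 months later | final study contact |

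At the start, exposure includes 1 to 12 months without ADR reports. At the end, ADRs can be recorded after exposure has stopped: Section 2 allows observation to go on after 1st line treatment ends if no 2nd line follows, and Safety Follow-up can add 30 days. The longest ADR window is 15 months plus 30 days, about 16 months. The shortest is a matter of weeks.

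**3. Proportion with an ADR by length of observation.** Formula: 1 − exp(−h·t). The hazards h are assumptions; the protocol gives none.

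| h per month | 3 months | 9 months | 15 months |
|---|---|---|---|
| 0.02 | 5.8% | 16.5% | 25.9% |
| 0.05 | 13.9% | 36.2% | 52.8% |
| 0.10 | 25.9% | 59.3% | 77.7% |

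**4. Two countries with the same hazard.** Assume 12 months of 1st line treatment, with consent at month 2 in one country and month 10 in the other. Observed time on treatment is 10 and 2 months.
- h = 0.02: 18% against 4%
- h = 0.05: 39% against 10%
- h = 0.10: 63% against 18%

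**5. A rate on the 9.3.1 exposure, if one were calculated.** With R months on treatment before consent and P months after it, the rate is multiplied by P/(R + P). This counts events on treatment only.
- R = 1, P = 15: 15/16 = 0.94
- R = 12, P = 15: 15/27 = 0.56
- R = 6, P = 6: 6/12 = 0.50
- R = 12, P = 3: 3/15 = 0.20
- R = 12, P = 1: 1/13 = 0.08

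In the example of step 4 with h = 0.05, the rates become 0.05 × 10/12 = 0.042 and 0.05 × 2/12 = 0.008 per month. Events recorded after 1st line treatment stops would enter the numerator without exposure and pull the other way.

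**6. Is a constant hazard tenable?** Section 7.1 gives a median of 10 days to the first dermatological symptom. If onset is exponential with that median (an assumption), the share of first onsets before the earliest possible consent, at about 30 days, is 1 − 2^(−30/10) = 87.5%. For skin reactions the risk after consent is thus not the risk at treatment start, and subjects enrolled at month 2 and month 10 are seen on different parts of the curve.

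**The case against.** Four arguments carry weight.

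- **No exposure-based rate is planned.** Section 9.3.1 never calls its exposure a safety denominator. For describing treatment patterns (9.7.2.4), counting from the first dose is right. A reader might infer that the protocol's ADR rate is wrong; the documents do not support that, because there is none. What stands is that the only exposure time on offer does not fit the ADR window.
- **The SAP may settle the denominator.** Section 9.7.1 refers further details to it, and it is not at hand, so the lack of a rate is not by itself a fault. But the protocol does state a scale in 9.7.3 and an exposure definition in 9.3.1, and an SAP that follows both inherits the difficulty.
- **Country distortion is conditional.** It requires enrolment timing or follow-up to differ by country. Section 9.9.1.1 expects reimbursement to produce different subject characteristics but says nothing about timing. That makes distortion plausible; it does not show that country comparisons are wrong.
- **The hazards are illustrative.** Section 9.7.3 names only ADRs leading to discontinuation of panitumumab and serious ADRs with a fatal outcome, a narrower set than ADRs in general. The percentages in the working are not predictions for those events.

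It would also be too strong to say that nothing is known about the time before consent, since earlier side effects are kept as medical history. And a single rate from consent would not make early and late enrollers comparable, because risk changes with time on treatment.

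**Conclusion.** The point holds in a limited form and is worth changing. A number of subjects is a weak measure for an incidence objective when ADR observation starts 1 to 12 months after the first dose and lasts from weeks to about 16 months. With equal risk, country figures may differ several-fold through timing alone (39% against 10% in the example), but only if timing differs between countries, and only under the assumed hazards and the assumed 12 months of treatment.

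The mismatch between 9.3.1 and 11.1.5.1 follows directly from the text. Its effect on an on-treatment rate, a factor of 0.94 down to 0.08, needs no hazard value for a given split of months, but it is the size of an error that would arise if such a rate were calculated. It is not an error in a planned result. The primary objective and the 4-point precision statement are not affected.

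**What to change.** **In 9.7.3**, keep the counts and add first-event incidence per 100 subject-months, in total and by country.
- Use one at-risk window: it starts at consent and ends at the earliest of the first event, the end of panitumumab treatment plus the protocol's existing 30-day safety follow-up, or final contact. Count only events inside it.
- Present the rate by time since first dose, or as cumulative incidence on that scale with delayed entry at consent.
- Show time from first dose to consent by country, so that readers can judge comparability.
- Report pre-consent side effects from medical history separately.
- State that subjects who stopped treatment before enrolment are not represented. Person-time from consent does not recover them.

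**In 9.3.1**, keep total exposure for treatment patterns, split it at consent, and state that time before consent is not an ADR denominator.

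**Reconcile first:** Section 9.2.8 starts the 30 days at the start of 2nd line treatment or at 15 months, while the footnote to Appendix E starts them at the end of 1st line treatment. The passages need to agree before the analysis window is written down.

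**Cost:** wording in two sections and a few table columns. The protocol already provides for the first-dose, consent, treatment-stop and end-of-study dates (9.1, 9.2.5 to 9.2.7, 9.7.2.4), and individual dose dates are not needed. The drawback is that any rate summary simplifies a changing risk, which is why the counts stay beside it.
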